6.7. Appendix 7: Details of Joint Count, HAQ-DI, and FACIT-F	
6.8. Appendix 8: List of Geographic Region	71
6.9. Appendix 9: Execution for Bayesian Model Averaging	72
6.9.1. R DREAMER Package to Execute BMA	72
6.9.2. BMA Components, Priors, and Weights	72
6.10. Appendix 10: List of Preferred Term for Herpes Zoster, Herpes Simplex, and Hepatitis B Virus	74
6.11. Appendix 11: Common Terminology Criteria for Adverse Events (CTCAE)	78
7. References	80

Table of Contents

Tables	Pa	ıge
Table KDAF.1.1.	SAP Version History Summary	.10
	Treatment Groups and Comparisons for Each Study Period and Analysis ulation	
	Description and Derivation of Efficacy and Patient Reported Outcome sures	34
Table KDAF.4.2.	Description of Efficacy and Patient Reported Outcome Analyses	.41

Table of Contents

Figure	Page
Figure KDAF.1.1	Study design. 17

Version History

Statistical Analysis Plan (SAP) Version 1 for Study J1A-MC-KDAF (KDAF) is based on the protocol dated 18 Jul 2022 and approved prior to unblinding.

Statistical Analysis Plan (SAP) Version 2 based on the protocol dated 31 May 2023 was approved prior to the primary outcome database lock and includes the following changes. Minor corrections/additions may not be included.

Section	Description of Change	Rationale
Section 1.2	Updated participant population	As per the protocol amendment (e)
Section 4.1	Added definition for safety analyses.	Safety analyses will be summarized by period, which requires baseline for each period.
	Added statement "If ET visit does not occur, last injection date will be considered as the end of the treatment period"	Clarification
	Added definition for analysis visit and data to be used for the analysis for eCOA assessments	To allow to use eCOA assessments collected within the visit window.
	Added "up to Week 24" and removed "within the same treatment period" for LOCF	To facilitate analysis in combined periods, Period 2 and Period 3A.
Section 4.4.2.1	Added methods handling missing data	Clarification
Section 4.4.3.2	Added estimand strategy and handling missing data	Clarification
Section 4.5	Added estimand strategy and handling missing data	Clarification
Section 4.6	Added periods and population for safety summary.	Safety analyses will be summarized by period.
	• Added statement "For Period 3B, the treatment groups will be combined and not be separated by populations"	Clarification

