What is the difference between peresolimab and placebo in the target patient population, in average change from baseline to Week 12 if all participants continued with treatment for 12 weeks without use of rescue or prohibited medications?

The estimand is described by the following attributes:

- Population: Participants with moderately-to-severely active RA
- Endpoint(s): Change from baseline for DAS28-hsCRP, SDAI, CDAI, 68 tender joint count (TJC68), 66 swollen joint count (SJC66), Physician's Global Assessment of Disease Activity (visual analog scale [VAS]), Patient's Global Assessment of Disease Activity (VAS), Patient's Assessment of Arthritis Pain (VAS), patient's assessment of physical function using the Health Assessment Questionnaire Disability Index (HAQDI), the duration and severity of morning joint stiffness, and Functional Assessment of Chronic Illness Therapy-Fatigue (FACIT-F) scores at Week 12

- How to account for ICEs: ICEs related to study intervention include the use of rescue or prohibited medication and ED from the study or study intervention. A hypothetical strategy will be used for these types of ICEs. Specifically, data collected after the first occurrence of ICE related to study intervention will be excluded from an analysis, and what the treatment effect would have been if rescued or prohibited medication(s) was not used, and all patients adhered to the treatment for 12 weeks will be estimated.
- Population-level summary: Difference in mean change from baseline to Week 12 between intervention conditions
- Rationale for estimand: The data collected after the treatment discontinuation, or the use of rescue or prohibited medication will not present the true efficacy effects.

Secondary estimand for categorical endpoints at Week 24 and Week 60

For secondary objectives that have categorical endpoints analyzed at Week 24 (or Week 60), the clinical question of interest is:

What is the proportion of achieving a successful response at Week 24 (or Week 60) in the target patient population without use of rescue or prohibited medications or discontinuing the study intervention?

The estimand is described by the following attributes:

- Population: Participants with moderately-to-severely active RA
- Endpoint(s): ACR20, ACR50, ACR70, DAS28-hsCRP LDA, DAS28-ESR LDA, SDAI LDA, CDAI LDA, DAS28-hsCRP remission, DAS28-ESR remission, SDAI remission, and CDAI remission at Week 24 (or Week 60)

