- How to account for ICEs: ICEs will be accounted using the same estimand strategy as for the primary estimand.
- Population-level summary: Proportion of participants achieving response at Week 24 (or Week 60) in each dosing regimen of peresolimab
- Rationale for estimand: Refer to the rationale for the primary estimand.

Secondary estimand for continuous endpoints at Week 24 and Week 60

For secondary objectives that have continuous endpoints analyzed at Week 12, the clinical question of interest is:

What is the average change from baseline to Week 24 (or Week 60) in the target patient population if all participants continued with treatment for 12 weeks without use of rescue or prohibited medications?

The estimand is described by the following attributes:

- Population: Participants with moderately-to-severely active RA
- Endpoint(s): Change from baseline for DAS28-hsCRP, SDAI, CDAI, TJC68, SJC66, and Physician's Global Assessment of Disease Activity (VAS) at Week 24 (or Week 60)

- How to account for ICEs: ICEs will be accounted using the same estimand strategy as for the secondary estimand for continuous endpoint at Week 12. It will be assumed that the same level of efficacy prior to the first ICE will continue, that is, last observation carried forward (LOCF) will be used for imputation.
- Population-level summary: Mean change from baseline to Week 24 in each intervention conditions
- Rationale for estimand: Refer to the rationale for the secondary estimand for continuous endpoints at Week 12.

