2.1. Multiplicity Adjustment

Adjustment for multiple comparisons will not be employed in the analysis for this study.

3. Analysis Sets

Abbreviations: CDAI = Clinical Disease Activity Index; LDA = low disease activity; Q4W = every 4 weeks; Q12W = every 12 weeks; SC = subcutaneous.

Table KDAF.3.1. Treatment Groups and Comparisons for Each Study Period and Analysis Population

Study Period	Analysis	Treatment Group	Abbreviation	Inferential
	Population			Comparison
Double-blind, placebo- controlled treatment period (Period 2)	mITT Population Safety Population	Placebo SC Q4W ^a Peresolimab 100 mg SC Q4W Peresolimab 400 mg SC Q4W Peresolimab 1000 mg SC Q4W	PBO PER100Q4W PER400Q4W PER1000Q4W	PER100Q4W vs. PBO PER400Q4W vs. PBO PER1000Q4W vs. PBO
Double-blind treatment period Weeks 12 to 24 (Period 3A)	Maintenance Population	Placebo SC Q4W to Peresolimab 400 mg SC Q4W Placebo SC Q4W to Peresolimab 1000 mg SC Q4W Peresolimab 100 mg SC Q4W Peresolimab 400 mg SC Q4W Peresolimab 1000 mg SC Q4W	PBO/PER400Q4W PBO/PER1000Q4W PER100Q4W PER400Q4W PER1000Q4W	No Between-Treatment Comparison
Double-blind treatment period Weeks 24 to 60 (Period 3B)	Maintenance Primary Population	Peresolimab 400 mg SC Q4W Peresolimab 400 mg SC Q12W Peresolimab 1000 mg SC Q4W Peresolimab 1000 mg SC Q12W	PER400Q4W PER400Q12W PER1000Q4W PER1000Q12W	No Between-Treatment Comparison
	Maintenance Secondary Population	Peresolimab 400 mg SC Q4W Peresolimab 1000 mg SC Q4W	PER400Q4W PER1000Q4W	No Between-Treatment Comparison
	Maintenance Tertiary Population	Placebo SC Q4W to Peresolimab 400 mg SC Q4W Placebo SC Q4W to Peresolimab 1000 mg SC Q4W Peresolimab 100 mg SC Q4W	PBO/PER400Q4W PBO/PER1000Q4W PER100Q4W	No Between-Treatment Comparison
Combined Periods 2 and 3A (Weeks 0 to 24)	mITT Population	Placebo SC Q4W to Peresolimab 400 mg SC Q4W Placebo SC Q4W to Peresolimab 1000 mg SC Q4W Peresolimab 100 mg SC Q4W Peresolimab 400 mg SC Q4W Peresolimab 400 mg SC Q4W Peresolimab 1000 mg SC Q4W	PBO/PER400Q4W PBO/PER1000Q4W PER100Q4W PER400Q4W PER1000Q4W	No Between-Treatment Comparison
Treatment Period (combined Periods 2 and 3; Weeks 0 to 60)	Safety Population (for exposure table)	Peresolimab 100 mg SC Q4W Peresolimab 400 mg SC Q4W Peresolimab 1000 mg SC Q4W	PER100Q4W PER400Q4W PER1000Q4W PER400Q4W/Q12W	No Between-Treatment Comparison

Study Period	Analysis	Treatment Group	Abbreviation	Inferential
	Population			Comparison
	Safety	Peresolimab 400 mg SC Q4W to Peresolimab 400 mg SC	PER1000Q4W/Q12W	

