Data collected after initiation of rescue or prohibited medication use will be handled according to the specified estimand strategy for efficacy analysis. Such data, unless otherwise noted, will be excluded from efficacy analyses, considered as missing, and handled according to a missing data imputation method as specified.

Missing data will be handled separately from estimand strategy. After intercurrent events related to study intervention are accounted for according to an estimand strategy specified in Section 1.1, any remaining missing data will be handled using the following missing data imputation methods:

• Nonresponder imputation (NRI):

When NRI is applied, participants with missing data will be considered as nonresponders regardless of whether they have at least 1 postbaseline data.

• LOCF:

When LOCF is applied, the last nonmissing observation up to Week 24 will be carried to the corresponding time point for evaluation. For participants who initiated rescue therapy, the last nonmissing observation prior to the initiation of rescue therapy will be carried forward. For randomized participants without any postbaseline observation, missing data will not be imputed.

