4.4.2. Secondary Endpoints and Analysis Methodology

The secondary endpoints at Week 12 in Period 2 include:

- Proportion of participants achieving:
 - o ACR50
 - o ACR70
 - o Remission or LDA in terms of DAS28-hsCRP
 - o Remission or LDA in terms of DAS28-ESR
 - o Remission or LDA in terms of SDAI, and
 - o Remission or LDA in terms of CDAI
- Mean change from baseline in:
 - o DAS28-hsCRP
 - o SDAI
 - CDAI
 - o TJC68
 - o SJC66, and
 - o Physician's Global Assessment of Disease Activity (VAS)
 - o Patient's Global Assessment of Disease Activity (VAS)
 - o Patient's Assessment of Arthritis Pain (VAS), and
 - o patient's assessment of physical function using HAQ-DI
 - Duration of morning joint stiffness
 - Severity of morning joint stiffness
 - FACIT-F scores
 - o Short Form-36 health survey acute form (SF-36) domains
 - o SF-36 Physical Component Summary, and
 - o SF-36 Mental Component Summary.

The secondary endpoints at Week 24 and Week 60 in Period 3 include:

- Proportion of participants achieving:
 - o ACR20
 - o ACR50
 - o ACR70
 - o Remission or LDA in terms of DAS28-hsCRP
 - o Remission or LDA in terms of DAS28-ESR
 - o Remission or LDA in terms of SDAI, and
 - o Remission or LDA in terms of CDAI
- Mean change from baseline in:
 - o DAS28-hsCRP
 - o SDAI
 - o CDAI
 - o TJC68
 - o SJC66, and
 - o Physician's Global Assessment of Disease Activity (VAS).

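### The SAP's only LOCF rule stops at Week 24, yet LOCF is the planned method for continuous endpoints at Week 60

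*SAP*

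**What the plan says.** The operational definition of LOCF is in SAP Section 4.1: "the last nonmissing observation up to Week 24 will be carried to the corresponding time point for evaluation". The next sentence deals with participants who start rescue therapy and has no Week 24 limit: "the last nonmissing observation prior to the initiation of rescue therapy will be carried forward".

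LOCF is then called on for Week 60 in three places:

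- **SAP Section 1.1**, estimand for continuous endpoints at Weeks 24 and 60. "It will be assumed that the same level of efficacy prior to the first ICE will continue", and LOCF is named as the means of doing this. The intercurrent events are those of the Week 12 continuous estimand: "ICEs related to study intervention include the use of rescue or prohibited medication and ED from the study or study intervention".
- **SAP Section 4.4.3.2**, which imputes any missing continuous value with LOCF in the supportive secondary summaries at Weeks 24 and 60.
- **SAP Table KDAF.4.2**, which specifies descriptive statistics with LOCF at Week 60 and at all other scheduled Period 3B visits.

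The SAP Version History gives the reason for the Week 24 wording: "To facilitate analysis in combined periods, Period 2 and Period 3A". Table KDAF.3.1 defines that combined period as Weeks 0 to 24 and Period 3B as Weeks 24 to 60.

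**The concern.** A cap at Week 24 suits an analysis that ends at Week 24. It does not suit Period 3B, which starts there. Read literally, it makes the programmer pass over every valid value between Week 24 and the missing visit.

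Two groups are affected:

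1. participants with no intercurrent event whose value at a Period 3B visit is missing;
2. participants whose first intercurrent event after Week 24 is prohibited medication or early discontinuation, because the uncapped sentence covers rescue only.

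The resulting Week 60 mean mixes Week 60 values with values from Week 24 or earlier. The error can go either way: worsening after Week 24 is hidden and further improvement is lost. The Q4W/Q12W assignment is made at Week 24 (SAP Section 1.2.1), so a Week 24 value placed in a Q12W column says nothing about Q12W dosing, although dosing frequency is one of the questions the study is meant to answer (SAP Section 1.2).

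**Working it through.** The plan states no figure to reproduce. The check traces the rule and then sizes it.

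**1. Which rule governs which participant at Week 60**

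| Participant | Governing text in SAP 4.1 | Value used at Week 60 | Agrees with Section 1.1? |
|---|---|---|---|
| Observed at Week 60, no prior event | none needed | the observed value | yes |
| Rescued after Week 24 | uncapped rescue sentence | last value before rescue | yes |
| Prohibited medication or early discontinuation after Week 24, no rescue | capped sentence | Week 24 or earlier | no |
| No event, Week 60 missing | capped sentence | Week 24 or earlier | Section 1.1 is silent; later valid data are discarded |

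Take two participants with the same history up to Week 40. One is rescued at Week 40 and carries the last value before Week 40. The other discontinues at Week 40 without rescue and carries Week 24 or earlier. Section 1.1 treats both as intercurrent events under one strategy.

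**2. Age of the carried value**

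- 60 − 24 = 36 weeks, the whole of Period 3B.
- Week 24 is Visit 9 (SAP Section 1.2) and Week 60 is Visit 18 (SAP Section 4.1). Visits 10 to 17 lie between, which is 8 visit numbers.
- Section 1.2 uses CDAI at two consecutive visits after Week 24, so later CDAI values do exist. The schedule of activities is not visible, so the count per measure is unknown.

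Illustration with invented values: CDAI is 8 at Week 24 and 17 at Week 52, and the participant discontinues without rescue after Week 52. The capped rule enters 8 at Week 60; the uncapped rule enters 17.

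**3. Endpoints affected**

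Section 4.4.2 lists 6 continuous secondary endpoints at Week 60: DAS28-hsCRP, SDAI, CDAI, TJC68, SJC66 and Physician's Global VAS. Table KDAF.4.2 adds Patient's Global VAS and Pain VAS: 6 + 2 = 8 measures.

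**4. Can values be missing without an intercurrent event?**

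Yes. Section 4.1 reports a date problem with electronic outcome assessments and uses a record only if its reassigned visit number matches the one in the system. Table KDAF.4.1 sets DAS28-hsCRP, SDAI and CDAI to missing if any component is missing. One excluded record can therefore blank all three scores in a participant still on treatment.

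**5. Size of the shift in a column mean**

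Shift = (share imputed under the cap) × (mean gap between the last valid value and the Week 24 value). Both inputs are assumptions.

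- Low: 0.10 × 2 = 0.2 CDAI points.
- High: 0.20 × 8 = 1.6 CDAI points.
- If such missingness is rare, at 2%: 0.02 × 2 = 0.04 to 0.02 × 8 = 0.16 points.

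If the gap is a worsening, the reported mean is too low by this amount; if it is an improvement, too high.

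**6. One participant in a small column**

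SAP Section 5 gives about 120 participants for each of the 400 mg and 1000 mg groups. Assume that 20–40% are re-randomized 1:1 at Week 24, that there is no attrition, and that these sets form the Maintenance Primary columns (the definition is not readable).

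- Column size: 120 × 0.20 / 2 = 12, to 120 × 0.40 / 2 = 24.
- One participant with a 2–8 point gap moves the mean by 2/24 = 0.08 to 8/12 = 0.67 points.

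**The case against.** **Order of operations.** Section 4.1 says intercurrent events are first handled under the Section 1.1 strategy, and LOCF then applies only to what is still missing. On that reading, Section 1.1 already settles prohibited medication and early discontinuation, with no cap. This shows what was probably intended, but it does not remove the conflict. Section 1.1 implements its assumption by naming LOCF, and Section 4.1 is the only visible place that defines LOCF. Nor does the argument reach participants without an event who miss a visit.

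**Another reading of the phrase.** It could limit the time points at which LOCF is used, leaving the source value free. Then Week 60 has no LOCF rule at all, although three places require one. According to the Version History, the phrase replaced a restriction to the same treatment period. That was a limit on the source value, which favours the literal reading. The sentence needs correcting either way.

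**Few participants are affected.** This largely stands. Participants without CDAI low disease activity at Week 24 go to rescue under Section 1.2, so their source value is generally Week 24 or earlier with or without the cap. Escape-rule discontinuations occur on rescue. Loss of low disease activity at two consecutive visits also leads to rescue, which makes the upper end of the CDAI gap less likely. Protocol Section 7.2 expects discontinuation to be uncommon. What remains is mainly Week 24 low-disease-activity achievers with later missing values and no rescue.

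**The point shifts are not from the documents.** Correct; they are illustrations only.

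**Conclusion.** The concern holds and is minor. The rule in Section 4.1 is wrong for Period 3B as written, because it fills Week 60 and other missing Period 3B values from Week 24 or earlier for anyone not covered by the rescue sentence. For prohibited medication and early discontinuation after Week 24, it also contradicts the Section 1.1 estimand.

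The 36-week gap, the 8 intervening visit numbers, and the 6 secondary endpoints (8 tabulated measures) follow from the documents. The CDAI shift of 0.2–1.6 points is conditional on the assumed share and gap, and could be well below that if non-rescue missingness is rare.

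Period 3B has no between-treatment comparison, so no test is affected. ACR, low disease activity and remission at Week 60 use nonresponder imputation. The primary Week 12 ACR20 analysis, the Week 12 MMRM analyses and the Week 24 results do not change. Participants rescued after Week 24 are not part of the error.

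**What to change.** Replace the LOCF sentence in SAP Section 4.1 with wording such as: *the last nonmissing observation up to the analysis time point will be carried forward; where the hypothetical strategy applies, only observations before the first intercurrent event are used.* This covers rescue, prohibited medication and early discontinuation with one rule and brings Section 4.1 into line with Section 1.1. The exception for participants with no postbaseline observation can stay.

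Optionally, footnote each Week 60 table with the number of imputed values.

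The cost is one SAP sentence, one programming rule and, if wanted, one footnote. It needs no new data or tables and changes no estimand or Week 24 result. Week 60 would still rest on single imputation, as it does now.

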4.2. Bayesian Model Averaging

A Bayesian model averaging (BMA) approach will be used to estimate the dose response relationship. This BMA approach is the Bayesian analog of the multiple comparisons procedure modeling (MCP-MOD) methodology (Bretz et al. 2005), and "the Qualification of the MCP-Mod procedure" (FDA 2015) is supportive in the use of MCP-MOD or BMA to assist in dose selection decisions.

BMA is a general mixture distribution, where each mixture component is a different parametric model. Prior weights are placed on each model and the posterior model weights are updated based on how well each model fits the data. Let $\mu(d)$ represent the mean of the dose response curve at dose d, $y = \{y_1, ..., y_n\}$ be the observed data, and $m \in \{1, ..., M\}$ be an index on the M parametric models described below. Then the posterior of the dose response curve, $\mu(d)$, of the BMA model is

$$p(\mu(d) \mid y) = \sum_{m=1}^{M} p(\mu(d) \mid y, m) p(m \mid y)$$
$$p(m \mid y) = \frac{p(y \mid m) p(m)}{\sum_{m} p(y \mid m^{*}) p(m^{*})}$$

where $p(\mu(d) \mid y, m)$ is the posterior mean dose response curve from model m, $p(m \mid y)$ is the posterior weight of model m, $p(y \mid m)$ is the marginal likelihood of the data under model m, and p(m) is the prior weight assigned to model m. In cases where $p(y \mid m)$ is difficult to compute, Gould (2019) proposes using the observed data's fit to the posterior predictive distribution as a surrogate in calculating the posterior weights; this is the approach used in this analysis.

4.2.1.1. BMA Analysis and Reporting

BMA analysis will be summarized by dose and provide:

- Observed response
- BMA estimated
 - Mean response
 - o SE and standard deviation of the mean response
 - o 2.5% and 97.5% quantiles
 - Summaries of posterior probability of LY-PBO treatment effect, that is, Prob(LY-PBO > EOI) where EOI is effect of interest

• Plot that includes observed response, BMA estimated response, and 2.5% and 97.5% posterior quantiles

BMA analysis will be summarized by component and model parameter and provide:

- Posterior mean
- SE and standard deviation of the posterior mean
- 2.5% and 97.5% posterior quantiles of the posterior distribution
- Convergence diagnostics
- Effective sample size
- Prior distributions
- Plot of the fitted BMA
- Plot of the BMA components

See Appendix 9 (Section 6.9) for execution details.

4.3. Participant Dispositions

A detailed description of participant disposition will be provided, including a summary of the number and percentage of participants entered into the study and randomized, the number and percentage of participants who complete the study or discontinue, both overall and by reason for discontinuation, and the frequency and percentage of patients who discontinued study treatment. A summary of important protocol deviations will be provided.

4.4. Efficacy Analyses

Table KDAF.4.1 includes the description and derivation of efficacy outcomes, including the primary and secondary efficacy outcomes.

Table KDAF.4.2 provides the detailed analysis plans, including estimand, analysis type, analysis method, missing data imputation, analysis population, timepoint, and treatment comparisons for the efficacy analyses.

4.4.1. Primary Endpoint and Analysis Methodology

The primary endpoint is the ACR20 response rate at Week 12.

ACR20 is defined as at least 20% improvement from baseline in both TJC (68 joint count; 0 to 68) and SJC (66 joint count; 0 to 66), and at least 20% improvement from baseline in at least 3 of the following assessments:

- Patient's Assessment of Arthritis Pain (VAS; 0 to 100 mm)
- Patient's Global Assessment of Disease Activity (VAS; 0 to 100 mm)
- Physician's Global Assessment of Disease Activity (VAS; 0 to 100 mm)
- Patient's Assessment of Physical Function as measured by the HAQ-DI (0 to 3 by 0.125)
- Acute Phase reactant as measured by high-sensitivity C-reactive protein (hsCRP) (mg/dL)

Refer to the algorithm in Appendix 6 (Section 6.6) to calculated ACR response.

The primary objective of this study is to test the null hypothesis that there is no difference in achieving ACR20 at Week 12 between peresolimab and placebo in patients with moderately-to-severely active RA.

Any missing data (for example, missing due to missing a visit) will be imputed using NRI for the primary analysis.

